12.3 END OF STUDY	20
13 REPORTING, PUBLICATIONS AND NOTIFICATION OF RESULTS.....	21
13.1 AUTHORSHIP POLICY	21
13.2 PUBLICATION.....	21
13.3 PEER REVIEW.....	21
14 REFERENCES.....	21

PROTOCOL APPROVAL

Longer term impact of COVID 19 infection in people with diabetes

Signatures

The undersigned confirm that the following protocol has been agreed and approved by the Sponsor and that the Chief Investigator agrees to conduct the study in compliance with this approved protocol and will adhere to the principles of GCP, the Sponsor SOPs, and any other applicable regulatory requirements as may be amended from time to time.

[name]
Chief Investigator

Signature

Date

[INSERT PI NAME]
[INSERT HEALTH BOARD
SITE NAME]
Principal Investigator

Signature

Date

LIST OF ABBREVIATIONS

AE	Adverse Event
BG	Blood Glucose
CI	Chief Investigator
CNORIS	Clinical Negligence and Other Risks Indemnity Scheme
COVID-19	Coronavirus SARSCOV-2
CRF	Clinical Research Facility
DMS	Data Management System
GCP	Good Clinical Practice
ICF	Informed Consent Form
NHS GGC	NHS Greater Glasgow and Clyde
ISF	Investigator Site File
NRS	NHS Research Scotland
PI	Principal Investigator
REC	Research Ethics Committee
SDG	Scottish Diabetes Group
SOP	Standard Operating Procedures
SMF	Study Master File

SUMMARY/SYNOPSIS

Study Title	Longer term impact of COVID 19 infection in people with diabetes (Short Title: Diabetes Long COVID study)	
Study Design	Observational Case Cohort study with Nested Case Control study	
Study Population	Adults with Type 1 and Type 2 Diabetes in Scotland	
Sample Size	Total sample size in Nested Case Control study, as per IRAS form: 1000 participants (500 cases and 500 matched controls, with at least 200 people in each of the categories of Type 1 and Type 2 diabetes)	
Planned Study Period	May 2021 to approximately October 2022	
Follow up phase duration	1 year (cases only)	
Aims	To understand the proportion of people with diabetes who experience longer term symptoms or illness after covid-19 infection, the nature of these symptoms, and the potential health impact of that.	
Primary	Objective: Case Cohort: After COVID infection, what proportion of people with type 1 and type 2 diabetes experience symptoms in the longer term (up to 18-24 months after index infection)?	Outcome Measures: The prevalence of symptoms in the longer term in people with diabetes up to 2 years after COVID-19 infection using Wellcome questionnaire
Secondary	Nested Case Control: What is the impact of "long COVID" upon physical activity, diabetes control and outcomes?	incremental walking test, hand grip, HbA1c
Inclusion Criteria	
Case* Cohort study:
 
 • Person with Diabetes (type 1 or type 2) • Aged 18 or over • Able to read and write in English 
*Cases additionally defined by self-reported COVID infection and or COVID test positive in clinical record
 
Nested Case Control study**:
 
**Cases defined by positive COVID test in the clinical record. Controls defined by no positive COVID test in clinical record or self-identified COVID infection.
	
Exclusion Criteria	
Nested Case Control study only:
 
 • Participating in the intervention phase of another clinical study 	

1 INTRODUCTION

Severe, longstanding symptoms may be experienced after COVID-19 infection. This study will complete both a matched case cohort study (online questionnaires) and a nested case control study (CRF visit), recruiting people with diabetes who have had evidence of COVID-19 infection along with age, sex and ethnicity matched controls with diabetes. We will examine prevalence and correlates of long COVID symptoms with biomarkers of inflammation, cardiometabolic risk and body composition. Participants who are cases will have a repeat study visit at 12 months.

2 BACKGROUND & RATIONALE

The COVID-19 crisis has posed an unprecedented challenge to health services world-wide. Early in the pandemic it became apparent that symptoms, sometimes severe, could persist after the acute illness. In an Italian study it was found that 55% of patients, questioned on average two months after symptom onset, were still experiencing three or more symptoms including tiredness, breathlessness and chest pain (1). “Long COVID” might be considered to be analogous to syndromes described after other viral illnesses and has been variously defined as “not recovering [for] several weeks or months following the start of symptoms that were suggestive of COVID, whether you were tested or not” (2), and more recently by NICE and SIGN as “Signs and symptoms that develop during or following an infection consistent with COVID-19, continue for more than 12 weeks and are not explained by an alternative diagnosis”. More recently an NIHR report suggested that there may be several overlapping post COVID syndromes underpinned potentially by direct effects on the heart, brain and indirect effects of prolonged hospitalisation (3).

People with diabetes are more likely to suffer severe adverse consequences of COVID-19 infection during the acute illness. In the Scottish population, people with diabetes are at considerably higher risk of having severe COVID-19 infection with odds ratio (OR) of fatal or critical care unit treated disease of 2.4 in type 1 diabetes and 1.4 in type 2 diabetes, with higher relative hazards in younger people with type 2 diabetes (4). Diabetes is also associated with an increased risk of in-hospital death following COVID in other populations (5). At this stage of the pandemic it is not clear whether there is also an increased susceptibility to longer term sequelae in people with diabetes. Risk scores have been developed to try to understand the likelihood of severe complications in acute illness both in diabetes (4) and the general population (6). Likelihood of longer term impact on health and economic factors will also be key in the public health response to COVID-19 and would ideally inform decisions as to the degree of shielding recommended for different groups of people in the population, including people with diabetes. Such information will also be key to the support of people with long-term consequences of COVID-19. Importantly however, chronic disease in general and diabetes and diabetes complications in particular, have well known effects on chronic wellbeing and association with depression, diabetes distress and related symptoms (7, 8). Understanding the effects of COVID in this population is therefore dependent on understanding the prevalence and architecture of symptoms in the *general* diabetes population.

In Scotland, information from clinical visits is held within the SCI Diabetes information system and, following additional data linkage to COVID-19 test results, this has allowed the detailed analysis of risks in the acute setting (4). We know that, to the end of July 2020, 2724 people with diabetes had had evidence of infection with COVID-19 (positive test, admission or death certificate) of whom 988 had unfortunately died. We expect therefore that conservatively there are at least 1736 people with diabetes in Scotland who may be living with the consequences of COVID-19. Understanding those consequences cannot be achieved with

routine electronic health record data and therefore this study will explore patient outcomes in people with diabetes compared to suitable controls. The study will use publicly available tools (Wellcome COVID questionnaire (9)) allowing cross comparison to other populations and to facilitate data sharing.

3 STUDY OBJECTIVES & OUTCOMES

To understand the proportion of people with diabetes who experience longer term symptoms or illness after COVID-19 infection, the nature of these symptoms, and the potential health impact of that.

The primary objectives of the study are:

After COVID infection, what proportion of people with type 1 and type 2 diabetes experience symptoms in the longer term (up to 18-24 months after index infection)?

The secondary objectives of the study are:

What is the impact of “long COVID” upon physical activity, diabetes control and outcomes?

4 STUDY DESIGN

4.1 INTERVENTION

This is a non-interventional study.

4.2 STUDY DESCRIPTION

We will recruit a large Case-Cohort of people with type 1 and type 2 diabetes in Scotland to assess the prevalence of symptoms after self-reported COVID infection. We will further recruit a nested case control study of those with positive COVID test in the clinical record (cases) and controls to examine physical measures, glycaemia and diabetes complications.

[figure not shown]
The cohort will be recruited predominantly from the NHS Research Scotland Diabetes Research Register with additional direct recruitment invited from clinic lists of those with previous evidence of COVID infection. This cohort will involve self-completed questionnaires and minimal personal information limited to contact details (e-mail, telephone) and not including patient identifiers such as name, address or CHI. The cohort will acknowledge “By ticking this box, you acknowledge that you have read the PIS and have had the opportunity to ask any and all questions to a research staff member” electronic checkbox prior to completion of demographic information and questionnaires.

The Nested Case Control study will be conducted in person under written consent and include:

[figure not shown]
- Blood sampling (for biomarkers and routine clinical measurements)
- Physical tests (incremental walk test, grip strength test)
- Waist and thigh measurement
- Bioimpedance measurement
- Pulmonary function test

Cases will repeat the CRF study visit approximately 1 year from the baseline visit.

4.3 STUDY FLOWCHART

4. applies to COVID cases and selected, matched controls

4.4 STUDY MATRIX

The study matrix is shown below.

Case cohort study (online questionnaires):

Approximate Week	Anytime (cases and controls)
Interest to participate	X
Remote Implied Consent (online)	X
Demographic information (online)	X
Questionnaires (online)	X
Option to self-nominate for Nested case control study via provision of contact email and/or phone number (online)	X

Nested case control study (CRF visit):

Approximate Week	-4 to 0	0 (cases and controls)	1 year (40-64 weeks: cases only)
Interest to participate	X		
Inclusion and exclusion assessed by research nurse		X	
Consent (written)		X	
Questionnaires (if not done previously) or repeat of Wellcome section 1.3		X	X
Blood sample for labs (optional)		X	X
Blood sample for routine clinical measures*		X	X
Grip strength test		X	X
Incremental walk test		X	X
Waist and thigh measurement		X	X
Bioimpedance (optional)		X	X
Pulmonary function test** (optional)		X	X
Extract of routinely collected healthcare data from SCI Diabetes system		X	X

*HbA1c, LFTs, lipids, U&Es

**Spirometry/FEV1

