4.5 STUDY ASSESSMENTS

Case-Cohort:

Self-completed, offered online (can be offered by phone/on paper for participants who request this).

1. Demographics
2. Questionnaires (in order of priority)
 - a. Wellcome Trust COVID 19 questionnaire (Most up to date version in use at the time of the study): This is a comprehensive instrument covering physical, cognitive, and mental health domains and will also allow comparison to developing UK reference population data). Questions deemed to require additional support have been removed.
 - b. Diabetes Related Quality of Life (DQOL)

- c. Diabetes-Specific [name]-1
 - d. EQ5D
3. Option to self-nominate for nested case control study.

Nested Case Control (CRF visit):

1. Written consent
2. Questionnaires (if not done previously) or Update of symptoms score Wellcome questionnaire section 1.3
3. Blood sample (optional) for research labs (16ml total, 6ml purple top (EDTA), 6ml gold top (serum), 4ml blue top (citrate)) for non-routine bloods: inflammatory (e.g. CRP), vascular (t-PA, vWF) and cardiac (hs troponin, NT proBNP) biomarkers consistently predictive of long-term adverse outcomes.
4. Blood sample (8ml total, 3ml purple top (EDTA) and 5ml gold top (serum)) for routine clinical measures (HbA1c, LFTs, lipids, U&Es).
5. Physical measures
 - a. Incremental walking test
 - b. Grip strength
6. Waist and thigh measurement
7. Bioimpedance (optional if site does not have this equipment)
8. Pulmonary function test (optional if site does not have this equipment)

Cases will be invited to a repeat study visit 1 year (40 to 64 weeks) from the initial study visit.

SOPs (shared from other studies) will be used to standardise:

- Incremental walk test
- Grip strength test
- Blood sampling, storage and shipment
- Pulmonary function test

Clinical data: Baseline and follow up data from SCI-Diabetes including glucose control and blood pressure.

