4.9 NUMBER OF PARTICIPANTS

The total number of participants required to complete the study is 500 cases and 500 age and sex matched controls in the nested case control study. This total number may be smaller or larger, depending upon the number of COVID-19 infections which have occurred in the population with diabetes during the timeframe of the study. Reasonable efforts will be made to enrol a matched control for each case participant who is willing to attend. Multiple controls may be enrolled if the first assigned control fails to complete all aspects of the study or is re-assigned as a case.

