4.10 INCLUSION CRITERIA

Case cohort study (online questionnaires):

- Person with Diabetes (Type 1 or Type 2)
- Aged 18 or over
- Able to read and write in English

Nested case control study (CRF visits):

- Cases defined by positive COVID test in the clinical record. Cases will be invited sequentially from the cohort but will be selected to include at least 200 people in each of the diabetes subgroups (type 1 diabetes or type 2 diabetes).
- Controls defined by no positive COVID test in clinical records and no reported infection by participant. Controls will be matched after matching of a limited demographic panel available from the panel (age in 5 year bands, ethnicity, sex, type of diabetes, SIMD quintile).

All participants attending a research facility must have completed a COVID safety check before attending in person, in line with local guidance. Cases will be post-COVID and at least 10 weeks post positive test result.

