2. **From diabetes clinic lists or database search (SCI Diabetes):** To augment recruitment of COVID test positive participants we will also screen clinic lists and recruit directly. A member of the study team will screen diabetes clinic lists (eg trak or local clinical system, when possible SCI Diabetes) which routinely have a note of previous COVID infection. Name and CHI noted on screening log (excel spreadsheet held on NHS computer). If patient declines this is noted and no further action. If patient assents to contact then contact information taken (telephone and email – if neither possible postal address) and added to screening log. Electronic data collection link sent by preferred means. If electronic remote data collection not possible then paper questionnaires will be made available by post or study team will discuss over the phone. Cases identified to by SCI Diabetes search will be approached in writing with Caldicott Guardian approval in place within a Health Board (likely to be used in selected Health Boards only).
3. We will also advertise the study by leaflets and posters and via newsfeed to My Diabetes My Way, allowing self-referral to the study team.

NESTED CASE-CONTROL RECRUITMENT:

Cases, by definition, will have had a positive COVID test present on the clinical record. Potential cases will be selected from the cohort where a record of self-reported COVID infection is presented. Potential cases will be invited to CRF visit by telephone or email. Where assent is given by phone the clinical record will be checked to confirm positive COVID test, visit is arranged, and PIS sent. All other study procedures will take place only after face-to-face written consent is obtained at the CRF visit.

Controls will be selected from the pool of people who have completed the online questionnaire information and who have indicated that they have not had a **positive** COVID test and do not believe that they have had COVID infection. Those who had possible infection but subsequent test negative are included. Matching will be by age (5 year category),

ethnicity, sex, SIMD quintile and type of diabetes included in the participant completed questionnaire.

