7.2 PROPOSED ANALYSES

An analysis plan will be prepared for the University of Glasgow Research Data Management department before the study closes, to detail what analysis will be performed on the data.

Case cohort study:

This includes **participant completed questionnaires only**. We will not have access to clinical record for whole group (limited to those in nested study) and will rely on patient self-report of COVID testing and infection to create groups. Analysis will be in three groups:

- a. Test positive COVID declared (**cohort A**)
- b. no test but self-declared COVID (**cohort B**)
- c. no COVID infection declared, including those with suspected infection but test negative (**control**)

Analysis of this data will include

1. **Frequency of COVID symptoms** (derived from question 1.3 Wellcome questionnaire: 28 domains answering yes/no for 0-28 score and by self-report at time of infection at 3 months and current (>3 months)).
 - a. **Primary analysis:** current score cohort vs control with adjustment for limited demographic panel: age band, ethnicity, sex, type of diabetes
 - b. Secondary analyses:
 - i. within cohort comparison of time of infection vs 3 months vs current
 - ii. comparison time of infection and 3 months vs current score of control (with adjustment)
2. **Other questionnaire data:** diabetes depression score, DQOL all of which are assessed currently only and will be assessed in cohort vs control.
3. Comparison of above end points in cohort B to cohort and controls.

NESTED CASE CONTROL STUDY

For this data, consent will allow access to confirm that patient is COVID test positive in the clinical record. Definitions and comparison will therefore be between:

Cases - COVID test positive in clinical record

Control - no previous clinical COVID infection reported by patient, no record positive COVID test.

Case vs control (First visit)

1. **Frequency of COVID symptoms** (derived from question 1.3 Wellcome questionnaire: 28 domains answering yes/no for 0-28 score and by self-report at time of infection at 3 months and current (>3 months)).
 - a. **Primary analysis:** current score case vs control with adjustment for age, sex, ethnicity, sex, type of diabetes, SIMD
 - b. Secondary analyses:
 - i. within cohort comparison of time of infection vs 3 months vs current
 - ii. comparison time of infection and 3 months vs current score of control (with adjustment)
 - iii. relationship of cycle threshold to symptom scores

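### Questionnaire and first-visit dates are neither tied between groups nor adjusted for, so calendar time can confound the cohort and first-visit comparisons of current symptoms

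*Protocol*

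**What the plan says.** - **Study period** (Summary/Synopsis): "May 2021 to approximately October 2022".
- **Online questionnaire** (4.4, case cohort table): "Anytime (cases and controls".
- **Nested first visit** (4.4, separate table): "0 (cases and controls", with interest recorded up to four weeks before. This is each participant's own clock. No calendar window is given, and no rule relates a control's visit to that of its case.
- **Matching, nested study** (4.10): "age in 5 year bands, ethnicity, sex, type of diabetes, SIMD quintile". Section 5.1 lists the same five factors, starting "Matching will be by age (5 year category".
- **Cohort primary analysis** (7.2): "current score cohort vs control with adjustment for limited demographic panel: age band, ethnicity, sex, type of diabetes". The nested first-visit primary analysis adds SIMD. Date is in neither set.
- **Recruitment** (4.2, 5.1): mainly from a research register of more than 14,000 people, with clinic-list or database screening added to find test-positive people, and self-referral.
- **Numbers** (4.9): the total may change "depending upon the number of COVID-19 infections which have occurred in the population with diabetes during the timeframe of the study". A matched control is sought for each attending case, with no time limit.
- **Replacement** (5.3, 5.6): controls found to be cases are moved and replaced, and controls with incomplete tests may be replaced.

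**The concern.** The outcome in both primary analyses is the symptom score at the time of answering. Symptoms such as cough, breathlessness, tiredness and low mood can plausibly vary with season, circulating infections and restrictions. If infected and control participants answer in different periods, that variation is read as an effect of COVID infection. A larger cohort does not shrink such a bias; it only makes the biased estimate more precise.

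This is more than a detail left to the analysis plan. Section 7.2 itself labels these analyses primary and names their covariates, and the timing of control visits is a matter of design. The point concerns the online comparison and the nested first-visit comparison. The one-year comparison (case second visit against control first visit) is a separate matter.

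**Working it through.** **1. The plan's own figure (7.1).** For two means, n per group = 2(z₀.₉₇₅ + z₀.₉₀)²/d². With d = 0.2 this is 2(1.960 + 1.282)²/0.04, just over 525, so 526. With d = 0.5 it is just over 84, so 85. Both stated figures reproduce with a two-sided test. At the planned 500 per group, power for 0.2 SD is 88.5%.

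**2. Length of the open window.** 1 May 2021 to 1 October 2022 is 17.0 months; to 31 October 2022 it is 18.0 months.

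**3. Where date could be controlled.**

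| Comparison | Date rule | Matching factors listed | Adjusted for |
|---|---|---|---|
| Cohort, current score | any time | none | age band, ethnicity, sex, diabetes type |
| Nested first visit, current score | week 0 on own clock | age band, ethnicity, sex, diabetes type, SIMD quintile | age, sex, ethnicity, diabetes type, SIMD |

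Calendar time appears in no cell.

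**4. Can dates differ in the cohort?** Section 7.2 groups people by COVID infection declared when they answer. That status only accumulates, so later responders are more likely to be in an infected group even if invitations go out evenly. Suppose equal numbers answer in each half of the study. The infected shares below are assumptions.

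| Infected share, early then late half | Infected answering late | Controls answering late | Gap |
|---|---|---|---|
| 20%, 30% | 30/50 = 60% | 70/150 = 47% | 13 points |
| 10%, 30% | 30/40 = 75% | 70/160 = 44% | 31 points |
| 10%, 40% | 40/50 = 80% | 60/150 = 40% | 40 points |

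**5. Can dates differ in the nested study?** Cases return 40 to 64 weeks after the first visit (4.5: "Cases will be invited to a repeat study visit 1 year (40 to 64 weeks) from the initial study visit"). If that visit has to fall within the planned period (an assumption), the last case first visit is between 25 December 2021 and 24 January 2022 at a 40-week gap, which is 7.8 to 8.8 months after the start. At 52 weeks it is 2 October to 1 November 2021. Control first visits have no such limit, and replacement controls necessarily come later than those they replace. Here the controls could be the later group, the reverse of step 4.

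**6. Size.** Bias = (difference between groups in the share assessed in a given period) × (symptom shift between periods, in SD). Neither input is in the documents. The false-positive rate uses the normal approximation with 500 per group, SE = √(2/500) = 0.063 SD.

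| Imbalance (assumed) | Period shift (assumed) | Bias | Share of 0.2 SD | False-positive rate |
|---|---|---|---|---|
| 0 | any | 0 | 0% | 5.0% |
| 0.1 | 0.1 SD | 0.01 SD | 5% | 5.3% |
| 0.3 | 0.2 SD | 0.06 SD | 30% | 15.8% |
| 0.4 | 0.3 SD | 0.12 SD | 60% | 47.5% |

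**The case against.** The strongest reply is that an open window shared by both groups biases nothing unless the dates differ, and the protocol does not say that they will. Register members are approached without regard to COVID status and classified from their own answers. Many potential cases existed before the study opened: section 2 counts at least 1736 people by the end of July 2020. In the nested study a control is sought for each case, and the interim look expects 50 cases and about 50 controls (6.1), which suggests broadly parallel accrual. Section 1.3 of the symptom questionnaire is also repeated at the visit, so open online timing need not carry into the nested score.

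Much of this stands, and it rules out several stronger readings that a reader might infer:

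- *The first visit is also open at any time over 17 months.* That wording heads only the questionnaire table, and step 5 shows that case first visits could be confined to the early months.
- *Cases answer later than controls, so the COVID effect is inflated.* Direction is not established, and in the nested study it may be the opposite.
- *Controls are all invited at launch.* No section says so.
- *The bias is a known share of the planned difference.* Any such figure multiplies two assumed inputs, and zero is possible.

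It does not remove the point. The cohort comparison has no pairing, equal counts are not equal dates, and accumulation (step 4) acts even when invitations are even. Repeating the symptom items at the visit moves the question to the visit date, which is also uncontrolled.

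**Conclusion.** The point holds in conditional form. Questionnaire and first-visit dates are not tied between groups, and calendar time is missing from the matching factors and from both adjustment sets named in 7.2. The protocol contains mechanisms by which dates can differ: accumulating infection status, the clinic-list route and later replacement of controls. Season and pandemic phase can therefore confound both primary comparisons of current symptoms.

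Size and direction cannot be computed from the documents. The illustrative range of 0.01 to 0.12 SD rests wholly on the assumed 10 to 40 point imbalance and 0.1 to 0.3 SD shift; with balanced dates the bias is zero. The case for change rests on the gap in the stated adjustment sets and the low cost of closing it, not on that range. A separate selection question, that people still uninfected late in the study may differ from those uninfected early, would not necessarily be solved by adjusting for date.

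**What to change.** - Keep the questionnaire completion date and the first-visit date with each record.
- In 7.2, add calendar period of completion (cohort) or of visit (nested first visit) to the adjustment sets, for example by month or quarter.
- Report the distribution of dates by group, so that readers can see how well the groups overlap. If overlap is poor, adjustment relies on extrapolation.
- In 4.10 or 5.1, state that each control's first visit will be booked close to that of its matched case where feasible. This should be a scheduling preference: a hard window on top of five matching factors could leave cases without controls.

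The cost is small. Over 18 calendar months, three-month periods use 18/3 − 1 = 5 degrees of freedom and months use 17, with a slight loss of precision. Some control visits may be booked a little later or earlier than otherwise.

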2. **Other questionnaire data:** diabetes depression score, DQOL all of which are assessed currently only and will be assessed in cohort vs control
3. **Walk test**
4. **Hand grip**
5. **Pulmonary function measures eg. FEV1**

Comparison of cases vs COVID positive cohort for demographics and main study measures.

Case vs control (First and second visit data)

1. **Frequency of COVID symptoms** (derived from question 1.3 Wellcome questionnaire: 28 domains answering yes/no for 0-28 score and by self-report at time of infection at 3 month, at time of first questionnaire, first visit and at second visit).
 - a. **Primary analysis:** second visit score case vs control (first visit) with adjustment for age, sex, ethnicity, sex, type of diabetes, SIMD
 - b. Secondary analyses:
 - i. within cohort comparison of time of infection vs all time points
 - ii. comparison time of infection and 3 months vs current score of control (with adjustment)
2. **Other questionnaire data:** diabetes depression score, DQOL all of which are assessed first and second visit cohort vs control (first visit)

3. **Walk test** first and second visit cohort vs control (first visit)
4. **Hand grip** first and second visit cohort vs control (first visit)
- Pulmonary function measures eg. FEV1** first and second visit cohort vs control (first visit)

B. Screening log. As above contain patient identifiers, will be held on NHS computers.

Output - acceptance rate for study

C. Study data - will be held within Redcaps platform. Outputs: process data on completion of the different modules of the study, final study dataset.

Key aspects will be

- a. Record of consent and electronic consent
- b. Ability to enter data to personal computer/ smartphone by participant
- c. Ability to enter separate data under same study ID for study visit
- d. Cloud exportable to SAS/ SPSS/ R

Analyses will be carried out by the study team using the statistical support offered by the University of Glasgow.

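### DQOL and distress are not re-collected at the CRF visits from people who already completed the online form, yet the nested analyses treat them as first- and second-visit values

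*Protocol*

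**What the plan says.** **Collection.** Protocol 4.4 (Study Matrix) has one questionnaire row for the nested study, marked at week 0 and at 1 year: "Questionnaires (if not done previously) or repeat of Wellcome section 1.3". Protocol 4.5 (Study Assessments) repeats the rule for the CRF visit: "Questionnaires (if not done previously) or Update of symptoms score Wellcome questionnaire section 1.3". The full set in 4.5 is the Wellcome questionnaire, DQOL, a one-item diabetes-specific scale (DDS-1 in 6.2) and EQ5D.

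**Who has already completed the form.** For controls, 5.1 states: "Controls will be selected from the pool of people who have completed the online questionnaire information". For cases, it states: "Potential cases will be selected from the cohort where a record of self-reported COVID infection is presented". Section 4.10 likewise invites cases in sequence from the cohort.

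**Timing.** The cohort matrix in 4.4 attaches no week to the online form; its single column is labelled "Anytime (cases and controls". The cohort criteria in 4.10 cover diabetes, age and language, and set no minimum time since infection. The only floor stands in the paragraph of 4.10 on attending a research facility: "Cases will be post-COVID and at least 10 weeks post positive test result".

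**Analysis.** Under the nested first-visit comparison, 7.2 lists "diabetes depression score, DQOL all of which are assessed currently only and will be assessed in cohort vs control", beside the walk test and hand grip. The next block, on first- and second-visit data, describes the same measures as taken from cases at both visits and compared with the controls' first visit.

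**The concern.** A contrast labelled as first visit, and listed with physical tests done that day, should rest on answers given at about that time. Here the schedule takes only the section 1.3 symptom items from a participant who has been through the online form. Their quality-of-life and distress values come from an earlier date that no rule limits.

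Two things are at stake:

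- **First visit.** The case-control difference in DQOL and distress can mix states from different times since infection, including times below the study's own floor for nested cases. It also cannot be set cleanly against the symptom score, walk test and grip measured on the day.
- **One year.** The planned second-visit analysis of these measures has no data behind it for the same people.

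An analysis plan could screen out early forms by date. It cannot recover visit values that were never collected, so the defect lies in the protocol's schedule.

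**Working it through.** **Step 1: what each route yields for DQOL and distress, reading 4.4 and 4.5 literally.**

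| Route | Visit 1 | 1-year visit (cases) |
|---|---|---|
| Online form already completed (normal route, both arms) | no new value; section 1.3 only | no new value; section 1.3 only |
| Form first completed at visit 1 | new value | no new value, since it has by then been done |

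Section 7.2 needs a visit value in both columns. The schedule supplies one in a single cell, the less usual route at visit 1. At 1 year a carried-over value would be at least 40 weeks old, because the repeat visit falls 40 to 64 weeks after the first. Within-case change would then be zero by construction.

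**Step 2: how early the form can be.** There is no minimum time from infection to form and no maximum gap from form to visit. Two features make early forms foreseeable:

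- 4.9 ties case numbers to infections occurring while the study runs.
- 5.1 sends the link to COVID-positive clinic patients with no waiting period.

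Under 5.3, a control later found to be a case moves to the case arm. That person's stored form may predate infection.

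**Step 3: scale.** The protocol's sample-size figures in 7.1 reproduce. With two-sided alpha 0.05 and 90% power, n per group = 2(1.960 + 1.282)²/d².

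- d = 0.2: 2 × 10.507/0.04 = 525.4, so 526.
- d = 0.5: 2 × 10.507/0.25 = 84.1, so 85.

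At the planned 500 per group the standard error of a difference in SD units is √(2/500) = 0.0632, and power for 0.2 SD is 88.5%. These figures serve only as a yardstick; the point does not depend on them.

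**Step 4: size of the shift.** Let f be the share of cases whose carried-over value differs from their state at the visit, and e the mean difference in SD. With controls taken as stable, the case-control difference moves by f × e. Neither f nor e is in the protocol; the values below are assumptions. The last column is the two-sided rejection rate if there is no true difference, Φ(fe/0.0632 − 1.96) + Φ(−fe/0.0632 − 1.96).

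| f | e (SD) | shift (SD) | share of 0.2 SD | rejection rate |
|---|---|---|---|---|
| 5% | 0.3 | 0.015 | 7% | 5.6% |
| 10% | 0.5 | 0.05 | 25% | 12.4% |
| 20% | 0.5 | 0.10 | 50% | 35% |

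A corner such as f = 30% with e = 1.0 would give 0.30 SD, but nothing in the protocol points to that combination.

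The sign is open. Forms from soon after the test would probably be worse than the visit state and widen the gap. Forms from before infection would tend to narrow it; f = 5% and e = 0.5 in that direction gives −0.025 SD. A mixture can cancel in part.

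**The case against.** **Carry-over is inferred.** No sentence says that the online value stands in for the visit value, and the second-visit wording of 7.2 suggests the authors meant to measure at both visits. That is fair, but under 4.4 and 4.5 no other value exists for someone who completed the form earlier. The conflict between sections needs resolving either way.

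**Most forms may be late.** A reader might infer that case values come from the acute illness. The documents do not support that as the general picture:

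- The background pool in section 2 was infected by the end of July 2020, about nine months before the planned start in May 2021.
- Clinic-list recruits are people with earlier evidence of infection.
- If the matrix row placing interest in the nested study at weeks −4 to 0 is the online self-nomination, the form falls about 10 − 4 = 6 weeks or more after the test. That is still below the floor, but not clearly acute.

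Acute-phase answers are therefore the extreme of what the text allows.

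**The arms do not differ by rule.** A reader might also infer that controls always answer online while cases answer partly at the CRF. Sections 4.10 and 5.1 draw cases from the cohort too, and the questionnaire row applies to both groups, so this does not hold.

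**Importance.** The nested primary comparison uses section 1.3, which is repeated at the visit. The synopsis names walk test, hand grip and HbA1c as the secondary measures. All of these are unaffected. This limits the reach of the point but does not remove it, because 7.2 plans explicit contrasts on DQOL and distress.

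**Conclusion.** The point holds as a collection defect and an internal conflict. Sections 4.4 and 4.5 do not produce the DQOL and distress values that 7.2 analyses at visit 1 for people who have already completed the form, nor at 1 year for anyone who has a baseline value. The nested contrasts on these measures must then use online forms of unrestricted date, which for cases may precede the 10-week floor or the infection itself.

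The conflict follows from the text alone. The size of any bias does not: it is f × e with both inputs unknown, running from negligible (0.015 SD) to a sizeable part of the design effect (0.10 SD, or half of 0.2 SD) under the illustrative values, in either direction. A fixed percentage inflation of the case deficit cannot be claimed.

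EQ5D is collected under the same rule, although the nested analyses in 7.2 do not name it.

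**What to change.** In 4.4 and 4.5, have every nested participant complete DQOL, the distress item and EQ5D at visit 1, and every case complete them again at the 1-year visit, whatever was done online before. In 7.2, state that the nested contrasts use only these visit values, so that the three sections agree.

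If burden rules this out at visit 1, use only online forms completed within a stated short window before the visit and, for cases, at least 10 weeks after the positive test, which is the protocol's existing floor. There is no equivalent fallback at 1 year: without a repeat there, the second-visit analysis of these measures has to be withdrawn.

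The cost is some extra participant time at visits already planned or, under the date limit, the loss of some records from the nested contrast.
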